An SAE based on ICH and European Union (EU) Guidelines on Pharmacovigilance for Medicinal Products for Human Use is any untoward medical occurrence that at any dose:

- Results in death
- Is life-threatening
(The participant was at risk of death at the time of the event. It does not refer to an event that hypothetically might have caused death if it were more severe.)
- Requires inpatient hospitalization or prolongation of existing hospitalization
- Results in persistent or significant disability/incapacity
- Is a congenital anomaly/birth defect
- Is a suspected transmission of any infectious agent via a medicinal product
- Is Medically Important*

*Medical and scientific judgment should be exercised in deciding whether expedited reporting is also appropriate in other situations, such as important medical events that may not be immediately life-threatening or result in death or hospitalization but may jeopardize the participant or may

require intervention to prevent one of the other outcomes listed in the definition above. These should usually be considered serious.

If a serious and unexpected AE occurs for which there is evidence suggesting a causal relationship between the study vaccine and the event (eg, death from anaphylaxis), the event must be reported as a serious and unexpected suspected adverse reaction even if it is a component of the study endpoint (eg, all-cause mortality).

Any ILI and complications related to ILIs fulfilling the criteria of an SAE will be reported as such during the entire study period from the first vaccination.

Unlisted (Unexpected) Adverse Event/Reference Safety Information

An AE is considered unlisted if the nature or severity is not consistent with the applicable product reference safety information. For INFLUENZA G1 mHA, the expectedness of an AE will be determined by whether or not it is listed in the IB.

ATTRIBUTION DEFINITIONS

Assessment of Causality

The causal relationship to study vaccine is determined by the investigator. The following selection should be used to assess all AEs.

Related

There is a reasonable causal relationship between study treatment administration and the AE.

Not Related

There is not a reasonable causal relationship between study treatment administration and the AE.

The term "reasonable causal relationship" means there is evidence to support a causal relationship.

By definition, all solicited AEs at the injection site will be considered related to the study vaccine administration.

SEVERITY CRITERIA

All AEs and laboratory data will be coded for severity using a modified version of the FDA grading table, based on version of September 2007 ([FDA 2007](#)), included in Section [10.5](#) Appendix 5, Toxicity Grading Scale.

For AEs not identified in the grading table, the following guidelines will be applied:

Grade 1	Mild	Symptoms causing no or minimal interference with usual social and functional activities
Grade 2	Moderate	Symptoms causing greater than minimal interference with usual social and functional activities
Grade 3	Severe	Symptoms causing inability to perform usual social and functional activities and requires medical intervention
Grade 4	Potentially life-threatening	Symptoms causing inability to perform basic self-care functions OR medical or operative intervention indicated to prevent permanent impairment, persistent disability OR emergency room visit or hospitalization

The severity of solicited signs and symptoms will be graded in the diary by the participant based on the severity assessment provided in the diary and then verified by the investigator using scoring system shown in [Table 6](#) and [Table 7](#) as follows (*Note*: severity of the measured events will be derived from the diameter [for erythema and swelling] and the temperature measurements [for fever]):

Adults/adolescents (≥ 12 years of age)

Table 6: Severity Assessment: Solicited Injection Site Events - Adults/Adolescents (≥ 12 years of age)

Grade	Definition
0	No pain/tenderness; Diameter of erythema, swelling < 25 mm.
1	Aware of symptoms but easily tolerated; Does not interfere with activity; Discomfort only to touch; Diameter of erythema, swelling ≥ 25 mm and < 50 mm.
2	Notable symptoms; Requires modification in activity or use of medications; Discomfort with movement; Diameter of erythema, swelling ≥ 50 mm and < 100 mm.
3	Incapacitating symptoms; Inability to do work, school, or usual activities; Use of narcotic pain reliever; Diameter of erythema, swelling ≥ 100 mm.
4	Hospitalization; Pain/tenderness causing inability to perform basic self-care function; For erythema, swelling: necrosis or exfoliative dermatitis.

Table 7: Severity Assessment: Solicited Systemic Events - Adults/Adolescents (≥ 12 years of age)

Grade	Definition
0	Absent; Fever/Pyrexia: Below 38.0°C or 100.4°F.
1	Minimal symptoms; Causes minimal or no interference with work, school, or self-care activities; Fever/Pyrexia: 38.0 - 38.4°C or 100.4 - 101.1°F.
2	Notable symptoms; Requires modification in activity or use of medications; Does NOT result in loss of work, school, or cancellation of social activities; Fever/Pyrexia: 38.5 - 38.9°C or 101.2 - 102.0°F.
3	Incapacitating symptoms; Requires bed rest or results in loss of work, school, or cancellation of social activities; Use of narcotic pain reliever; Fever/Pyrexia: 39.0 - 40.0°C or 102.1 - 104.0°F.
4	Hospitalization; Inability to perform basic self-care functions; Fever/Pyrexia: Greater than 40°C or 104.0°F.

SPECIAL REPORTING SITUATIONS

Safety events of interest on a sponsor study vaccine in an interventional study that may require expedited reporting or safety evaluation include, but are not limited to:

- Overdose of a sponsor study vaccine
- Suspected abuse/misuse of a sponsor study vaccine
- Accidental or occupational exposure to a sponsor study vaccine
- Medication error, intercepted medication error, or potential medication error involving a Johnson & Johnson medicinal product (with or without patient exposure to the Johnson & Johnson medicinal product, eg, product name confusion, product label confusion, intercepted prescribing or dispensing errors)
- Exposure to a sponsor study vaccine from breastfeeding
- Reporting of participant pregnancy or participant partner(s) pregnancy

Participant-specific special reporting situations should be recorded in the eCRF. Any special reporting situation that meets the criteria of an SAE should be recorded on the SAE page of the eCRF.

PROCEDURES

All Adverse Events

All AEs, regardless of seriousness, severity, or presumed relationship to study vaccine, must be recorded using medical terminology in the source document and the eCRF. Whenever possible, diagnoses should be given when signs and symptoms are due to a common etiology (eg, cough, runny nose, sneezing, sore throat, and head congestion should be reported as "upper respiratory infection"). Investigators must record in the eCRF their opinion concerning the relationship of the AE to study therapy. All measures required for AE management must be recorded in the source document and reported according to sponsor instructions.

For all studies with an outpatient phase, including open-label studies, the participant must be provided with a "wallet (study) card" and instructed to carry this card with them for the duration of the study indicating the following:

- Study number
- Statement, in the local language(s), that the participant is participating in a clinical study
- Investigator's name and 24-hour contact telephone number
- Local sponsor's name and 24-hour contact telephone number (for medical personnel only)
- Site number
- Participant number
- Any other information that is required to do an emergency breaking of the blind

Serious Adverse Events

All SAEs that have not resolved by the end of the study, or that have not resolved upon discontinuation of the participant's participation in the study, must be followed until any of the following occurs:

- The event resolves
- The event stabilizes
- The event returns to baseline, if a baseline value/status is available
- The event can be attributed to agents other than the study vaccine or to factors unrelated to study conduct
- It becomes unlikely that any additional information can be obtained (participant or health care practitioner refusal to provide additional information, lost to follow-up after demonstration of due diligence with follow-up efforts)

Suspected transmission of an infectious agent by a medicinal product will be reported as an SAE. Any event requiring hospitalization (or prolongation of hospitalization) that occurs during the course of a participant's participation in a study must be reported as an SAE, except hospitalizations for the following:

- Hospitalizations not intended to treat an acute illness or AE (eg, social reasons such as pending placement in long-term care facility)
- Surgery or procedure planned before entry into the study (must be documented in the eCRF). *Note:* Hospitalizations that were planned before the signing of the ICF, and where the underlying condition for which the hospitalization was planned has not worsened, will not be considered SAEs. Any AE that results in a prolongation of the originally planned hospitalization is to be reported as a new SAE.

The cause of death of a participant in a study, whether or not the event is expected or associated with the study vaccine, is considered an SAE.

Information regarding SAEs will be transmitted to the sponsor using an SAE reporting form and the eCRF form for AEs, which must be completed and reviewed by a physician from the study site, and transmitted in a secure manner to the sponsor immediately, but no later than 24 hours of their knowledge of the event. The initial and follow-up reports of an SAE should be transmitted in a secure manner electronically or by facsimile (fax). Telephone reporting should be the exception and the reporter should be asked to complete the appropriate form(s) first.

CONTACTING SPONSOR REGARDING SAFETY

The names (and corresponding telephone numbers) of the individuals who should be contacted regarding safety issues or questions regarding the study are listed in the Contact Information page(s), which will be provided as a separate document.

PRODUCT QUALITY COMPLAINT HANDLING

A PQC is defined as any suspicion of a product defect related to manufacturing, labeling, or packaging, ie, any dissatisfaction relative to the identity, quality, durability, or reliability of a product, including its labeling or package integrity. A PQC may have an impact on the safety and efficacy of the product. Timely, accurate, and complete reporting and analysis of PQC information from studies are crucial for the protection of participants, investigators, and the sponsor, and are mandated by regulatory agencies worldwide. The sponsor has established procedures in conformity with regulatory requirements worldwide to ensure appropriate reporting of PQC information; all studies conducted by the sponsor or its affiliates will be conducted in accordance with those procedures.

Procedures

All initial PQCs must be reported to the sponsor by the study-site personnel immediately, but no later than 24 hours after being made aware of the event.

If the defect is combined with an SAE, the study-site personnel must report the PQC to the sponsor according to the SAE reporting timelines (refer to Section 8.3.1, Time Period and Frequency for Collecting Adverse Event and Serious Adverse Event Information). A sample of the suspected product should be maintained for further investigation if requested by the sponsor.

Contacting Sponsor Regarding Product Quality

The names (and corresponding telephone numbers) of the individuals who should be contacted regarding product quality issues are listed in the Contact Information page(s), which will be provided as a separate document.

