8.3.2. Method of Detecting Adverse Events and Serious Adverse Events

Care will be taken not to introduce bias when detecting AEs or SAEs. Open-ended and nonleading verbal questioning of the participant is the preferred method to inquire about AE occurrence.

Solicited Adverse Events

Solicited AEs are used to assess the reactogenicity of the study vaccine and are predefined local (at the injection site) and systemic events for which the participant is specifically questioned and which are noted by participants in their diary.

After each vaccination, participants will remain under observation at the study site for at least 30 minutes for presence of any acute reactions and solicited events. In addition, participants will record solicited signs and symptoms in a diary for 7 days post-vaccination. All participants will be provided with a diary and instructions on how to complete the diary (see Overview in Section 8, Study Assessments and Procedures). The site staff will verbatim transcribe the information provided by the participant into the relevant sections of the eCRF. Review of diary entries with participants and grading of symptoms must be done by a qualified and delegated site staff member under the oversight of the investigator or a delegated physician. After review of the diary entries with the participant, the investigator or qualified delegate, will complete their own assessment and document it in the relevant sections of the eCRF. Once a solicited sign or symptom from a diary is considered to be of severity Grade 1 or above, it will be recorded as a solicited AE.

Solicited Injection Site Adverse Events

Participants will be asked to note in the diary occurrences of injection site pain/tenderness, erythema, and swelling at the study vaccine injection site daily for 7 days post-vaccination (day of vaccination and the subsequent 7 days). The extent (largest diameter) of any erythema and swelling should be measured (using the ruler supplied) and recorded daily. The case definitions for solicited injection site events can be found in Section 11, References ([Gidudu 2012](#); [Kohl 2007](#)).

Solicited Systemic Adverse Events

Participants will be instructed on how to record daily temperature using a thermometer provided for home use. Participants should record the temperature in the diary in the evening of the day of vaccination, and then daily for the next 7 days approximately at the same time each day. If more

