## **5.6.1. Adverse Events**

### **5.6.1.1. Definitions**

Solicited AEs are used to assess the reactogenicity of the study vaccine and are predefined local events (pain/tenderness, erythema, and swelling at the injection site) and systemic events (fatigue, headache, nausea, myalgia, and fever) for which the participant is specifically questioned, and which are noted by participants in their reactogenicity diary. Unsolicited AEs are all AEs for which the participant is not specifically questioned.

Solicited AEs shown in the tables are extracted from the investigator assessment pages (CE) of the CRF. For unsolicited AEs, only the AEs within the 28-day period following each vaccination will be presented in the safety tables. SAEs will be captured and tabulated in the outputs covering the whole study period. All other collected unsolicited adverse events will be presented through listings.

The verbatim terms used in the eCRF by investigators to identify AEs will be coded using the Medical Dictionary for Regulatory Activities (MedDRA).

Solicited administration site symptoms will be considered as related to the study vaccine.

The severity of the AEs will be classified as grade 1 to 4. Solicited events that are graded less than grade 1, are not considered as AE. In case no grades are available, the grading of the solicited events will occur according to the grading list in Appendix 6.

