**5.6.1.4. Missing Data**

Missing data will not be imputed. Participants who do not report an event will be considered as participants without an event. An AE with a missing severity or relationship will be considered as an AE reported, but will be considered as not reported for the severity or relationship. For example,

an AE with missing severity will be considered as an AE reported for the analysis of any grade but will be considered as not reported for the analysis of at least grade 3.

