## 6.6. Appendix 6 Guidance for Industry: Toxicity Grading Scale for Healthy Adult and Adolescent Volunteers Enrolled in Preventive Vaccine Clinical Trials

Refer to the Appendix 5 of the CTP for Toxicity Grading Scale.

The laboratory values provided in Appendix 5 of the CTP serve as guidelines and are dependent upon institutional normal parameters. Institutional normal reference ranges should be provided to demonstrate that they are appropriate.

If a laboratory value falls within the grading as specified below but also within the local laboratory normal limits, the value is considered to be normal and will be reset to grade 0.

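### Protocol Table 6 and Appendix 5 grade solicited erythema and swelling differently at exactly 50 mm and 100 mm, and the SAP fallback for ungraded events leads to Appendix 5, not to the table investigators use

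*Protocol*

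**What the plan says.** Protocol 10.4, Severity Criteria, names two scales. The general rule reads: "All AEs and laboratory data will be coded for severity using a modified version of the FDA grading table", and that table is Appendix 5 (protocol 10.5). The rule for solicited signs and symptoms is separate. Participants grade them in the diary, and the grades are "then verified by the investigator using scoring system shown in" Tables 6 and 7. A note adds that severity for erythema and swelling comes from the measured diameter.

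In Table 6 the Grade 3 diameter is "Diameter of erythema, swelling ≥ 100 mm". In Appendix 5 the erythema and swelling rows, both marked as revised by the sponsor, place 100 mm at the top of Grade 2.

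SAP 5.6.1.1 states the analysis source: "Solicited AEs shown in the tables are extracted from the investigator assessment pages (CE) of the CRF". It then gives a fallback: "In case no grades are available, the grading of the solicited events will occur according to the grading list in Appendix 6". SAP Appendix 6 (section 6.6) has no injection-site scale of its own. It says: "Refer to the Appendix 5 of the CTP for Toxicity Grading Scale".

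**The concern.** Severity of solicited local events is part of the primary endpoint (protocol section 3, SAP 5.3.1). SAP 5.3.3 tabulates it by worst grade and as at least Grade 3. For erythema and swelling the diameter alone decides Grades 1 to 3, so the handling of a boundary value is the definition of the grade.

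Two things do not line up. The protocol applies two scales with different boundaries to the same events and gives no order of precedence. The SAP then sends events without a grade to the scale that investigators are not told to use for solicited events. Within one table, two participants with the same 100 mm reading could appear in different grades, depending only on whether the investigator's grade was filled in.

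**Working it through.** **Inputs.** Diameter cut-offs from protocol 10.4 Table 6, and from the erythema and swelling rows of protocol 10.5 Appendix 5:

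| Grade | Table 6 | Appendix 5 |
|---|---|---|
| 1 | at least 25, below 50 mm | 25 to 50 mm |
| 2 | at least 50, below 100 mm | 51 to 100 mm |
| 3 | 100 mm or more | above 100 mm |

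Grade 4 does not depend on diameter in either table. Appendix 5 has no Grade 0 row; readings below 25 mm are taken here as ungraded, which matches Table 6.

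**Step 1: compare the scales.** Every whole-millimetre diameter from 0 to 200 was graded under both. They differ at two values only:

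| Diameter | Table 6 | Appendix 5 | At least Grade 3 changes? | Any grade changes? |
|---|---|---|---|---|
| 50 mm | 2 | 1 | no | no |
| 100 mm | 3 | 2 | yes | no |

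Both differences are one grade, and Appendix 5 is the lower each time. If fractions of a millimetre were recorded, Appendix 5 would also leave readings between 50 and 51 mm without a grade, where Table 6 gives Grade 2. The documents do not state the recording precision.

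**Step 2: follow the fallback.** SAP 5.6.1.1 leads to SAP Appendix 6, and that leads to protocol Appendix 5. A 100 mm reading graded by an investigator with Table 6 is Grade 3. The same reading graded by the fallback is Grade 2.

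**Step 3: look for a rule that settles it.** SAP 5.6.2 assigns values that fall in a gap of the grading scale to the adjacent worse grade. It is worded for laboratory results, and 50 mm and 100 mm lie in no gap: each scale grades them. It does not help.

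**Step 4: size of one reclassification.** Active groups have 25 participants, and the pooled placebo group has 10 + 10 = 20 (protocol Table 1; pooling in SAP section 2). One participant moved across the Grade 3 line changes that group's percentage by 1/25 = 4 points, or 1/20 = 5 points. This is the effect per event. The documents give no frequency for such readings.

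**The case against.** The strongest reply is that protocol 10.4 largely answers the question itself: a general rule for all events is followed by a dedicated rule for solicited ones, and on an ordinary reading the dedicated rule governs. That is a fair reading, and it narrows the protocol conflict. It does not remove the SAP problem, because the SAP fallback points to the general scale.

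The second reply is that the fallback will hardly ever be used. The tables draw on investigator pages, and protocol 8.3.2 records a diary sign as a solicited event "Once a solicited sign or symptom from a diary is considered to be of severity Grade 1 or above", so a recorded event should normally carry a grade. To change a result, the grade must be missing, the diameter must be present and exactly 50 or 100 mm, and the reading must be the participant's worst. This stands and is why the expected effect is small. The diary's grading scale and the programming specifications are not in the documents, so practice cannot be checked.

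Two stronger readings are tempting, and the documents do not support them.

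- A reader might infer that SAP 5.6.1.4 contradicts the fallback, since there "an AE with missing severity will be considered as an AE reported for the analysis of any grade" but not for at least Grade 3. The two rules fit in sequence: derive the grade where a diameter exists, and treat it as missing otherwise. Grading a recorded diameter is derivation, not imputation.
- A reader might infer that 24-hour reporting of related Grade 3 events (protocol 8.3.1) or pausing criterion 6 (protocol 6.8) is compromised. Both act on grades assigned at the site, so the SAP fallback cannot touch them. They would be affected only if a site applied Appendix 5 in place of Table 6. Criterion 6 also needs three participants with the same event type persisting at Grade 3 for longer than 3 consecutive days, its sentinel limb covers systemic events only, and the sponsor's medical officer or designee decides on any pause. The consequence is remote.

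**Conclusion.** The inconsistency is certain on the text and narrow in reach. The two protocol scales differ by one grade at exactly 50 mm and exactly 100 mm, and the SAP fallback adopts the scale that gives the lower grade at both. Only the 100 mm boundary affects the tables of events of at least Grade 3. The expected effect on reported results is small. That judgement assumes whole-millimetre recording and few missing investigator grades; the first is not stated, and the second is made likely by protocol 8.3.2. The point is still worth correcting, because it concerns the definition of a primary-endpoint severity grade and the SAP, followed as written, departs from the protocol's own rule for solicited events.

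**What to change.** The sponsor reconciles Table 6 and Appendix 5 to one set of diameter cut-offs for erythema and swelling; which set is the sponsor's choice. In the SAP, the fallback in 5.6.1.1 and 6.6 for solicited events is redirected to the same table that investigators use. Investigator-page grades remain the analysis source.

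The SAP change is one cross-reference and needs no new data. It should be made before the database lock for the final analysis. A count of ungraded erythema or swelling readings at exactly 50 or 100 mm would show whether any output is affected. Reconciling the protocol tables needs an amendment if it changes what sites do, because protocol 10.3 does not allow a clarification communication to alter study conduct.
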